7.3.2. Planned Other Efficacy Statistical Analyses

7.3.2.1. Time to Onset and Time to First COPD Exacerbation

| Statistical Analyses |
|---|
| Endpoint(s) |
| 
 • Time to Onset (an increase of 100mL in FEV1 above baseline) during 0-6 h post-dose on Day 1 • Time to First COPD Exacerbation |
| Model Specification |
| 
 • Cox's proportional hazards model • Terms in the model: 
 Dependent variable: Time to Onset or time to first COPD exacerbation Categorical: treatment group, smoking status (screening), and Country^[1]. • Use the 'exact' method for handling ties. (If the analysis will not run using the 'exact' method, then the 'Efron' method for handling ties will be used instead.) |
| Model Checking & Diagnostics |
| 
 • Refer to Appendix 12: Model Checking and Diagnostics for Statistical Analyses. |
| Model Results Presentation |
| 
 • Hazard ratios for each of the treatment comparisons with associated 95 % CIs and p-values, will be presented. • Kaplan-Meier survivor functions of the proportion of subjects with onset over time will be obtained for each treatment group separately and will be plotted on the same figure. • The median time to onset on Day 1 (taken from the Kaplan Meier analysis) will also be presented in the summary table. |
| Example SAS code |
| 
 • Cox's proportional hazards model |

| Statistical Analyses |
|---|
| <pre>proc phreg data=dsetin ; model timeto1*eventflag(0)=treatment smokehis country^[1] / risklimits ties=exact; run; • Kaplan-Meier survivor functions proc lifetest data=wdw outsurv=survest; time timeto1*eventflag(0); strata treatment; run; quit;</pre> |

Note: [1]: In China subgroup analysis, Country will be removed.

7.3.2.2. Proportion Endpoints

| Statistical Analyses |
|---|
| Endpoint(s) |
| Model Specification |
| 
 Proportion Achieving Increase in FEV1 of $\geq 12\%$ and ≥ 200 mL above Baseline at any Time During 0-6 h Post-dose on Day 1 Proportion Achieving Increase of ≥ 100 mL above Baseline in Trough FEV1 Proportion of Responders According to TDI Focal Score |
| Proportion Endpoints 
 Logistic Regression Model At each of Days 2, 28, 56, 84, 112, 168 and 169, the proportion of subjects who achieved an increase of 100 mL above baseline in trough FEV1 will be analysed using a separate logistic regression model. At each visit, the proportion of responders according to TDI focal score will be analysed using a separate logistic regression model. Terms in the model: Dependent Variable : Proportion Categorical : Treatment, Smoking Status (screening), Country^[1] Continuous : Baseline FEV1 or BDI |
| Model Checking & Diagnostics 
 Refer to Appendix 12: Model Checking and Diagnostics for Statistical Analyses. |
| Model Results Presentation 
 For each treatment comparison, the odds ratio, 95 % CI and p-value will be presented. |
| Example SAS code <pre>proc logistic data=fevaanal descending; class treatment (ref='1') smokehis country^[1] / param=ref; model respond=treatment base smokehis country^[1] / clodds=wald expb; ods output logistic.oddsratios=odds1 (where=(index(effect,'TREATMENT')>0)</pre> |

| Statistical Analyses |
|---|
| <pre>or index(effect,'treatment')>0)); ods output logistic.parameterestimates=pval1 (keep=probchisq variable classval0 where=(variable in ('TREATMENT', 'treatment'))); run;</pre> |

Note: [1]: In China subgroup analysis, Country will be removed.

7.3.2.3. Serial FEV1/FVC and Trough FVC

| Statistical Analyses |
|--|
| Endpoint(s) |
| 
 Serial FEV1 (including post dose 15 and 30 min, 1, 3 and 6 h post-dose measurements on Day 1) Trough FVC (including Days 2, 28, 56, 84, 112, 168 and 169) Serial FVC (including post dose 15 and 30 min, 1, 3 and 6 h post-dose measurements on Day 1) |
| Model Specification, Checking, Results Presentation and SAS code |
| 
 Similar to trough FEV1 in Section 7.1.2 |
| Model Checking & Diagnostics |
| 
 Refer to Appendix 12: Model Checking and Diagnostics for Statistical Analyses. |

7.3.2.4. Rescue Salbutamol Use (mean puffs/days)

| Statistical Analyses |
|--|
| Endpoint(s) |
| 
 Rescue Salbutamol Use (mean puffs/days) (absolute and change from baseline value) |
| Model Specification |
| 
ANCOVA model
 
 The mean number of puffs of rescue medication per day over each four weeks of treatment and the entire 24 week treatment period will be analyzed. Terms in model: 
 Response : Rescue Salbutamol Use (mean puffs/days) (absolute or change from baseline value) Fixed Categorical : Treatment, Smoking Status, Country^[1] Fixed Continuous Covariates : Baseline Baseline is defined in Section 10.6.5 Rescue Use part. Two models will be fitted; one with absolute value and one with change from baseline value. |
| Model Checking & Diagnostics |
| 
 Refer to Appendix 12: Model Checking and Diagnostics for Statistical Analyses. |
| Model Results Presentation |
| 
 LS means and LS mean change from baseline values for each treatment group will be presented with their associated standard errors. Estimated treatment differences along with corresponding 95 % CIs and p-values will be presented for the treatment comparisons. |
| Example SAS code |

| Statistical Analyses |
|----------------------|
|----------------------|

```

proc mixed data=start;
  by week;
  class treatment smokehis country[1];
  model endpoint=treatment baseline smokehis country[1];
  lsmeans treatment / cl diff e om;
  ods output lsmeans=lsmeans;
  ods output diffs=diffs;
run;

```

Note: [1]: In China subgroup analysis, Country will be removed.

7.4. Health Outcomes Analyses

7.4.1. Overview of Planned Health Outcomes Analyses

Health outcomes analyses will be based on the Modified Intent-To-Treat population, for the analysis on all countries overall and on China Modified Intent-To-Treat population for the analysis on China subgroup alone, unless otherwise specified.

Table 6 provides an overview of the planned health outcomes analyses, with further details of data displays being presented in [Appendix 14: List of Data Displays](#). All the planned study population analyses will be done on all countries overall, and China subgroup alone (with the exception of those displays specified by country).

Table 6 Overview of Planned Health Outcomes Analyses

| Endpoint | Absolute | | | | | | | | Change from Baseline | | | | | | | |
|--|----------------|---|---|---------|------------------|------------|------------------|----------------|----------------------|---|---------|---|------------|---|--|---|
| | Stats Analysis | | | Summary | | Individual | | Stats Analysis | | | Summary | | Individual | | | |
| | T | F | L | T | F | F | L | T | F | L | T | F | F | L | | |
| Baseline SGRQ (Total and each domain) | | | | Y | | | Y ^[1] | | | | | | | | | |
| SGRQ total score | Y | | | Y | | | Y | Y | Y | | Y | Y | | | | Y |
| SGRQ each domain score | | | | Y | | | Y | | | | Y | | | | | |
| Proportion of responders according to SGRQ total score | Y | | | Y | | | | | | | | | | | | |
| Baseline COPD Assessment Test (CAT) score | | | | Y | | | | | | | | | | | | |
| CAT score | Y | | | Y | Y ^[2] | | Y | Y | | | Y | | | | | Y |
| Proportion of Responders according to CAT Score | Y | | | Y | | | | | | | | | | | | |
| Healthcare Resource Utilisation | | | | Y | | | Y | | | | | | | | | |

NOTES :

- T = Table, F = Figure, L = Listing, Y = Yes display generated.
- Stats Analysis = Represents TFL related to any formal statistical analyses (i.e. modelling) conducted.
- Summary = Represents TFL related to any summaries (i.e. descriptive statistics) of the observed raw data.
- Individual = Represents FL related to any displays of individual subject observed raw data.
- All the tables will be presented by treatment group.
- [1]: Only total baseline score will be listed.
- [2]: Two scatter plots will be generated:
Change from baseline CAT score at day 168 vs Change from baseline FEV1 at 168
Baseline CAT scores versus baseline FEV1

7.4.2. Planned Health Outcomes Statistical Analyses

| Primary Statistical Analyses |
|--|
| Endpoint(s) |
| Model Specification, Checking, Results Presentation and SAS code |
| 
SGRQ, CAT score
 
 • Similar to trough FEV1 in Section 7.1.2 
Proportion of responders according to SGRQ total score Proportion of Responders according to CAT Score
 
 • Similar to proportion endpoint in Section 7.3.2.2 |

8. SAFETY ANALYSES

8.1. Adverse Events Analyses

8.1.1. Overview of Planned Adverse Events Analyses

The safety analyses will be based on the Modified Intent-To-Treat population, for the analysis on all countries overall and on China Modified Intent-To-Treat population for the analysis on China subgroup alone, unless otherwise specified.

In case of treatment misallocation, additional outputs for safety analyses may be provided, showing the subjects impacted by misallocation and the treatments they actually received.

Table 7 provides an overview of the planned analyses, with further details of data displays being presented in [Appendix 14: List of Data Displays](#). All the planned study population analyses will be done on all countries overall, and China subgroup alone (with the exception of those displays specified by country).

Table 7 Overview of Planned Adverse Event Analyses

| Endpoint | Absolute | | |
|--|----------|---|------------|
| | Summary | | Individual |
| | T | F | L |
| Exposure | | | |
| Exposure to Study Treatment | Y | | Y |
| Adverse Events (AEs) | | | |
| Overview of AE incidence | | | |
| All AEs by SOC | Y | | Y |
| Common AEs by Overall Frequency | Y | Y | |
| All Drug-Related AEs by SOC | Y | | |
| Subject Numbers for Individual AEs | | | Y |
| Relationship Between AE SOCs, PT & Verbatim Text | | | Y |
| On-Treatment AEs by SOC | Y | | |
| Post-Treatment AEs by SOC | Y | | |
| On-Treatment AEs experienced by 3% (after rounding) or more of subjects in any treatment group | Y | | |
| Common On-Treatment non-serious AEs ^[1] | Y | | |
| On-treatment Drug-Related AE's | Y | | |
| On-treatment Non-Serious Drug Related Adverse Events | Y | | |
| All AEs | | | Y |
| Serious and Other Significant AEs | | | |
| Fatal SAEs ^[1] | Y | | Y |
| Non-Fatal SAEs | Y | | Y |
| Pre-treatment fatal SAEs | Y | | |
| Pre-treatment non-fatal SAEs | Y | | Y |
| On-treatment non-fatal SAEs | Y | | Y |
| Post-treatment Non-fatal SAEs | Y | | Y |
| SAEs by SOC | Y | | |
| Drug related serious AE | Y | | |

| Endpoint | Absolute | | |
|---|----------|---|------------|
| | Summary | | Individual |
| | T | F | L |
| Drug related SAEs by SOC | | | Y |
| Pre-treatment AEs leading to withdrawal from the study | Y | | Y |
| On-treatment AEs leading to permanent discontinuation of study treatment or withdrawal from the study | Y | | Y |
| On-Treatment AE of Special Interest | Y | | Y |
| Fatal SAE of Special Interest | Y | | |
| On-treatment Non-Fatal SAE of Special Interest | Y | | |
| Drug Related Fatal SAEs | Y | | |
| On-treatment Non-Fatal Drug Related SAEs | Y | | |
| Reasons for potential ELLIPTA malfunctions | | | Y |

- T = Table, F = Figure, L = Listing, Y = Yes display generated.
- Summary = Represents TFL related to any summaries (i.e. descriptive statistics) of the observed raw data.
- Individual = Represents FL related to any displays of individual subject observed raw data.
- All the tables will be presented by treatment group.

[1]: A cut-off of 3% for 'common' will be used, but for this purpose it should be applied without rounding, i.e. an event experienced by 2.8% subjects should not be included. This table also needs a 'number of subjects with any event' row which only counts subjects experiencing any event in the body of the table.

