8.3.1. Analysis Populations

Four subject populations will be identified.

The **All Subjects Enrolled** Population will comprise all subjects, for whom a record exists on the study database, including screen failures and any subject who was not screened but experienced an SAE between the date of informed consent and the planned date of the Screening Visit. This population will be used for reporting subject disposition, reasons for withdrawal prior to randomization, and inclusion, exclusion and randomization criteria deviations and SAEs for non-randomized subjects.

The **Screen and Run in Failure** population will comprise all subjects in the All Subjects Enrolled Population who are recorded as screen failures or run-in failures in the electronic case report form (eCRF). It will be used for the tabulation of reasons for screen and run-in failure and for inclusion, exclusion and randomisation criteria failed.

The Modified **Intent-to-treat** (ITT) Population will comprise all subjects randomized to treatment who received at least one dose of randomized study medication in the treatment period. Randomized subjects will be assumed to have received study medication unless definitive evidence to the contrary exists. Outcomes will be reported according to the randomized treatment allocation. This population will constitute the primary population for all data analyses and displays. All scheduled data collected until the time of study discontinuation will be included in the Modified Intent-to-treat analysis for subjects who withdraw from the study.

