4. ANALYSIS POPULATIONS

Population for analysis to be performed on all subjects enrolled from China and Korea.

| Population | Definition / Criteria | Analyses Evaluated |
|---------------------------|--|--|
| All Subjects Enrolled | 
 • Comprise of all subjects, for whom a record exists on the study database, including pre-screen/screen failures and any subject who was not screened but experienced an SAE between the date of informed consent and the planned date of the Screening Visit. | 
 • Reporting subject disposition, AE listing and treatment misallocations listing |
| Screen and Run in Failure | 
 • Comprise of all subjects in the All Subjects Enrolled Population who are recorded as screen failures or run-in failures in the electronic case report form (eCRF) | 
 • Tabulation of reasons for screen and run-in failure and for inclusion, exclusion and randomisation criteria failed |
| Modified Intent-To-Treat | 
 • Comprise of all subjects randomized to treatment who received at least one dose of randomized study medication in the treatment period. • Randomized subjects will be assumed to have received study medication unless definitive evidence to the contrary exists. • Outcomes will be reported according to the randomized treatment allocation. • All scheduled data collected until the | 
 • Constitute the primary population for all data analyses and displays. |

| Population | Definition / Criteria | Analyses Evaluated |
|--------------|--|--|
| | time of study discontinuation will be included in the Modified Intent-to-treat analysis for subjects who withdraw from the study. | |

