10.1.3. Programmed Checks to Identify Non-medication Deviations

The data checks identified in [Table 11](#) will be performed to further identify protocol deviations.

Table 11 Programmed non-medication checks

| Reason for exclusion | Check performed | Deviation Type |
|---|--|--|
| Age | (visit date – date of birth) < 40 at pre-screening | Full |
| Smoking history | number of pack-years < 10 at screening ^[1] or only use a pipe and/or cigar | Full |
| Severity of disease: FEV1/FVC | Pre-salbutamol or Post-salbutamol FEV ₁ /FVC ≥0.7 or any one missing at screening | Full |
| Severity of disease: % predicted | Pre-salbutamol or Post-salbutamol FEVPDPC > 70% or any one missing at screening | Full |
| Dyspnea (mMRC) | mMRC < 2 at screening or missing | Full |
| COPD exacerbation during run-in | Exacerbation onset date between dates of screening and start of treatment | Full |
| Compliance with treatment | Overall compliance < 80 % or > 120 % or missing | Full |
| Incorrect treatment | At any point | Partial; data excluded from start of incorrect treatment onwards |
| Blind broken ^[3] | At any point | Partial; data excluded from date of breaking of blind |
| COPD exacerbation during treatment and not withdrawn | Exacerbation onset date between treatment start and stop date +1 with measurement of primary efficacy endpoint after onset date ^[2] | Partial; data excluded from date of onset onwards |
| Meet other withdrawn criteria defined in the protocol but not withdrawn | Manual Review | Partial; data excluded from date of PD happened. |
| Trough FEV1 outside window | 23 h or 24 h FEV1 assessment outside window of 22.5-24.5h after previous day's dose | Time-point specific |

Note:

1. Pipe and/or cigar use cannot be used to calculate pack-year history.
2. Subject experiences an exacerbation during the treatment period requiring the use of any systemic or oral corticosteroids with prescribed or non-prescribed (self-administered) antibiotics, and/or requiring emergency treatment or hospitalisation. If subjects used either prescribed or non-prescribed (self-administered) antibiotics only for the treatment of exacerbation, they were permitted to remain in the study under PI's discretion according to the study protocol therefore the use of only antibiotics will not be defined as a protocol deviation.
3. Subjects whose blind was broken by someone external to GSK (i.e. site staff).

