10.5.3. Reporting Process & Standards

| Reporting Process | |
|---|---|
| Software | |
| 
 The currently supported versions of SAS software will be used. | |
| Reporting Area | |
| HARP Server | : uk1salx00175 |
| HARP Area | : \arenv\arprod\gsk573719\ac4117410\final |
| QC Spreadsheet | : arenv\arprod\gsk573719\ac4117410\final\qc |
| Analysis Datasets | |
| 
 Analysis datasets will be created according to Integrated Data Standards Library standards. | |
| Generation of RTF Files | |
| 
 RTF files will be generated. | |

| Reporting Standards | |
|---|--|
| General | |
| 
 The current GSK Integrated Data Standards Library (IDSL) will be applied for reporting, unless otherwise stated: 
 4.03 to 4.23: General Principles 5.01 to 5.08: Principles Related to Data Listings 6.01 to 6.11: Principles Related to Summary Tables 7.01 to 7.13: Principles Related to Graphics | |
| Formats | |
| 
 All data will be reported according to the randomized treatment the subject received unless otherwise stated. However, there may be additional adhoc displays for individual subjects using the actual treatment received. GSK IDSL Statistical Principles (5.03 & 6.06.3) for decimal places (DP's) will be adopted for reporting of data based on the raw data collected. Numeric data will be reported at the precision collected on the eCRF. The reported precision from non eCRF sources will follow the IDSL statistical principles but may be adjusted to a clinically interpretable number of DP's. | |
| Planned and Actual Time | |
| 
 Reporting for tables, figures and formal statistical analyses : 
 Planned time relative to dosing will be used in figures, summaries, statistical analyses and calculation of any derived parameters, unless otherwise stated. Reporting for Data Listings: 
 Planned and actual time relative to study drug dosing will be shown in listings (Refer to IDSL Statistical Principle 5.05.1). Unscheduled or unplanned readings will be presented within the subject's listings. | |
| Unscheduled Visits | |
| 
 Unscheduled visits will not be included in summary tables except as part of a 'worst case post-baseline' assessment. | |

| Reporting Standards | |

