10.6.3. Safety

Extent of Exposure

- Number of days of exposure to study drug will be calculated based on the formula:

$$\text{Duration of Exposure in Days} = \text{Overall Treatment Stop Date} - \text{Overall Treatment Start Date} + 1$$
- If there are any treatment breaks during the study, exposure data will be adjusted accordingly.
- If overall treatment stop date is missing it will be imputed as follows:
 - For subjects who attended a Study Treatment Discontinuation visit, use the date of the Study Treatment Discontinuation visit
 - For subjects who attended the last on-treatment visit, use the Visit 8 (Week 24) date.
 - For subjects who died and did not attend a Study Treatment Discontinuation visit or the last on-treatment visit, use the date of death
 - For all other subjects, use the last recorded exposure start or stop date.
- If a subject's overall exposure start date is missing then it will be assumed to be their Day 1 visit date.
- If a subject received a treatment other than the randomised treatment during the study, the exposure will still be calculated based on overall exposure start and stop dates.

Adverse Events

- The most frequent on-treatment AEs will be defined as the on-treatment AEs experienced by 3 % (after rounding) or more of subjects in any treatment group.
- AE groups of special interest have been defined as AEs which have specified areas of interest for UMEC. The following table presents the special interest AE groups and subgroups. The complete list, including the PTs which contribute to each of the groups will be provided by Global Clinical Safety and Pharmacovigilance (GCSP) using the MedDRA version current at the time of reporting. This will be finalized prior to unblinding.

| Special Interest AE Group | Special Interest AE Subgroup |
|--|--|
| Cardiovascular effects | Cardiac Arrhythmia Cardiac Failure Cardiac Ischaemia Hypertension Stroke |
| Urinary Retention | |
| Pneumonia | |
| Anticholinergic syndrome | |
| Gastrointestinal obstruction | |
| Hypersensitivity | |
| LRTI excluding pneumonia | |
| Ocular effects (antimuscarinic) | |
| Paradoxical bronchospasm | |
| gallbladder disorders | |
| 
 • A flag will be derived to identify on-treatment AEs of special interest. In order to ensure consistency with the umeclidinium Global ISS, all outputs will use the same MedDRA version (i.e. v 15.0) and the same list of special interest terms as was used for the umeclidinium Global ISS. | |

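### Safety tables follow the randomised arm even when the other treatment was taken, and as-treated safety output is only optional, so misallocation would put some events under the wrong treatment

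*SAP*

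**What the plan says.** **Population.** SAP 8.1.1 states: "The safety analyses will be based on the Modified Intent-To-Treat population". SAP 8.2.1 and 8.3.1 repeat this for laboratory data, vital signs and ECG. Protocol 8.3.1 says of the same population: "This population will constitute the primary population for all data analyses and displays".

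**Arm.** For Modified ITT, SAP 4 says: "Outcomes will be reported according to the randomized treatment allocation". The reporting standards in SAP 10.5.3 agree: "All data will be reported according to the randomized treatment the subject received unless otherwise stated".

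**Misallocation.** The as-treated provisions are permissive. SAP 8.1.1 says that "additional outputs for safety analyses may be provided, showing the subjects impacted by misallocation and the treatments they actually received", and SAP 10.5.3 that "there may be additional adhoc displays for individual subjects using the actual treatment received".

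**Exposure.** For a subject who received something other than the randomised treatment, SAP 10.6.3 says that "the exposure will still be calculated based on overall exposure start and stop dates". SAP 10.6.2 treats compliance in the same way.

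**Contrast with efficacy.** In the Per Protocol analysis, incorrect treatment has a fixed rule in SAP 10.1.3: "Partial; data excluded from start of incorrect treatment onwards".

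**The concern.** Analysis by randomised arm protects the efficacy comparison, because it keeps the groups that randomisation created and its errors tend to be conservative for a superiority claim. For safety the same rule is not conservative. If some placebo-randomised subjects took UMEC, their UMEC events are counted as placebo events. If some UMEC-randomised subjects took placebo, the UMEC rate is diluted. Either way, a true difference in an event rate is expected to look smaller than it is.

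Safety against placebo is a stated objective (Protocol 2), and allocation is 2:1, so the placebo column is the smaller one and moves more per subject.

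Timing also matters. SAP 1 says that analysis decisions are made before unblinding, but SAP 10.1 makes an exception for incorrect containers, whose contents are confirmed only once the blind is broken. Permissive wording therefore leaves room for the choice of as-treated safety output to be made when arms and events are visible. A rule fixed in advance removes that room.

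**Working it through.** No figure in the plan is in dispute. The check is of the text, followed by a simple illustration of size.

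**Text**

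1. SAP 4 defines four populations: All Subjects Enrolled, Screen and Run in Failure, Modified ITT and Per-Protocol, each with a China counterpart. None is as-treated.
2. Safety Tables 3.1 to 3.48 (SAP 10.14.8) use Modified ITT, except Tables 3.11, 3.12 and 3.19, which cover screen and run-in failures. No table is by treatment received.
3. Modified ITT is reported as randomised, and exposure runs over the overall start and stop dates. Both the event and the days on the wrong product therefore go to the randomised arm.
4. Two fixed listings show who was affected: Listing 3 (planned and actual treatments) and Listing 27 (misallocations). Neither gives incidence by treatment received.

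**Size**

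Inputs: 192 UMEC and 96 placebo subjects planned (Protocol 5.2), and 81 placebo subjects planned in China (Protocol 8.2.1). The number misallocated is not given in either document, so it is an assumption.

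*One affected subject with an event:*
- placebo column: 1/96 = 1.04 percentage points
- UMEC column: 1/192 = 0.52 percentage points
- China placebo column: 1/81 = 1.2 percentage points

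*Expected attenuation.* Let m placebo-randomised subjects take UMEC throughout, with true event rates pU and pP. The tabulated placebo rate is expected to be [(96 − m)·pP + m·pU]/96, so

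expected tabulated difference = (1 − m/96) × (pU − pP).

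With assumed rates of 10% on UMEC and 5% on placebo, the true difference is 5.0 points:

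| m | Calculation | Tabulated difference (points) |
|---|---|---|
| 0 | 5.0 × 96/96 | 5.00 |
| 1 | 5.0 × 95/96 | 4.95 |
| 5 | 5.0 × 91/96 | 4.74 |
| 10 | 5.0 × 86/96 | 4.48 |

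These rows assume that the wrong treatment was taken for the whole study. An ELLIPTA holds 30 doses (Protocol 5.1), so a single wrong inhaler covers about 30/168 = 18% of the treatment period, and only events in that window would be misplaced.

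**The case against.** The strongest reply is that this is a contingency of unknown and possibly zero size. Packs are assigned centrally through RAMOS NG, and neither document predicts any misallocation. The SAP also provides more than one optional output. Listings 3 and 27 identify affected subjects, Listing 14 gives exposure and Listing 16 gives all adverse events, so a reader of the report could trace every case. All of that stands, and it keeps the severity down. It does not supply a re-tabulation, and it leaves the decision to produce one open.

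Three stronger readings are tempting but not supported:

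- *The error always pulls the arms together.* This holds only in expectation. A placebo-randomised subject who takes UMEC and has no event lowers the placebo rate. A UMEC-randomised subject who takes placebo and has a background event raises the UMEC rate. With one to three subjects, the observed gap can move either way.
- *A few misallocated subjects could hide a signal through the 3% threshold for common events.* Three subjects on placebo give 3/96 = 3.1%, but the threshold applies to any treatment group and only decides which rows are shown. Reaching it adds a row. Tables 3.3 and 3.5 show adverse events with no threshold.
- *The absence of an IDMC makes this worse.* No interim analysis is planned, and SAP 3.2 releases the randomisation codes only after database freeze. How the final tables are grouped has no bearing on monitoring during the trial.

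**Conclusion.** The point holds as a defect in a stated rule. If a subject takes the other treatment, the planned safety tables will credit that subject's events and exposure to the randomised arm, and nothing in the SAP requires a corrected table. The SAP foresees the situation in its deviation, compliance and exposure rules and in Listing 27, yet it fixes a rule for Per Protocol efficacy and leaves safety to discretion.

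The effect is small for isolated cases: about 1 percentage point of placebo incidence per affected subject with an event. On the assumed 10% and 5% rates, the expected loss is about 0.05 of a 5-point difference for each placebo subject on UMEC throughout. It is zero if no misallocation occurs. The direction is towards no difference in expectation only. Severity is low to moderate. The case for acting is that the remedy is cheap and can be fixed before anyone sees the data by arm.

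**What to change.** Before unblinding, state in SAP 4 and SAP 8 that Modified ITT safety displays are by treatment actually received. Tables 3.11, 3.12 and 3.19 are unaffected. Add a fixed rule for subjects who took both treatments: for example, attribute each event to the treatment being taken at onset, split exposure in the same way, say how such subjects count in the denominators, and list the events concerned. Assigning each subject to the treatment taken for most of the study would not be enough, because one wrong 30-dose inhaler would leave the subject in the randomised arm and the tables unchanged.

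At minimum, turn the permissive wording in SAP 8.1.1 into a commitment, and name the as-treated tables to be produced if any misallocation occurs: exposure, adverse events, serious adverse events and adverse events of special interest.

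Keep randomised allocation for all efficacy displays. The cost is one derived variable and some SAP wording. Safety and efficacy denominators may differ by a few subjects, which a footnote can explain. Sample size is unaffected.
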